9.4.2 Biomarker investigations

This section was changed in Amendment 2, see Section 15.1 for details.

Biomarker investigations in the present study will include the biomarkers listed below.

Mandatory (sampled at all time points):

- NT-proBNP (baseline disease status & efficacy)
- High sensitivity troponin T (hs-TNT) (baseline disease status)
- Cystatin C (baseline disease status & efficacy)
- Free fatty acid (FFA) (target engagement / mechanistic marker)
- Urine albumin-to-creatinine ratio (UACR)
- Hemoglobin A1c (HbA1c) (target engagement / mechanistic marker)
- Neutrophil gelatinase-associated lipocalin (NGAL) (baseline disease status & efficacy)

Additional exploratory biomarker sampling:

- Soluble suppression of tumorigenicity-2 (sST2) (baseline disease status & efficacy)
- Galectin-3 (Gal-3) (baseline disease status & efficacy)
- Growth differentiation factor 15 (GDF-15) (baseline disease status & efficacy)
- Mid-regional pro-atrial natriuretic peptide (MR-proANP) (baseline disease status & efficacy)
- Copeptin (baseline disease status & efficacy)
- Osteopontin (OPN) (baseline disease status & efficacy)
- Tissue inhibitor of metalloproteinase-4 (TIMP-4) (baseline disease status & efficacy)
- Additional newly emerging HF or safety biomarkers

Blood sampling for biomarkers is scheduled for the time points as given in Section 9.1. All biomarkers will be measured using validated assay systems. Quality control (QC) and calibration samples will be analyzed concurrently with study samples. The results of the QC samples will be reported in a separate analytical report. Details on the collection, processing, storage and shipment of biomarker samples will be provided in separate documents (e.g. sample handling sheets or lab manual). Additional exploratory biomarkers sampling is to be used for research purposes to identify and / or verify biomarkers that are predictive or correlate with the efficacy / safety and the response in terms of tolerability of neladenoson bialanate. The analysis of exploratory biomarker may include the listed above exploratory biomarkers, safety biomarkers or new emerging HF biomarkers. Exploratory biomarker statistics may be reported separately. Exploratory biomarker analysis completed in the first year after the end of the study will be reported back to the investigator, if this provides additional meaningful information. Pure exploratory measures without an established interpretation might be withheld of reporting, considering that this will be of no value to the investigator or patient. The steering committee will provide guidance to the sponsor on reporting of exploratory biomarkers to investigators and patients.

In addition to the biomarkers listed above, other biomarkers deemed relevant to gain further knowledge about the pathomechanism of the disease or about the drug (i.e. mode of action related effect or safety of the drug) may be measured, based on newly emerging data from other ongoing studies and / or literature data.

Table 9–2: Sample types used for biomarker investigations

Sample type, short form	Description
Biomarker serum	Blood sample for serum preparation for biomarker analysis
Biomarker plasma	Blood sample for plasma preparation for biomarker analysis
Biomarker urine	Urine sample for biomarker analysis

9.4.3 Clinical efficacy variables

9.4.3.1 Clinical outcome events

The following clinical outcome events will be collected:

- All deaths (CV and non-CV)
- HF hospitalizations and urgent visits for HF
- Myocardial infarction
- Stroke

The CEC will adjudicate all deaths as either CV or non-CV, and other events listed above in accordance with the pre-specified endpoint criteria in the adjudication charter. Investigators are mandated to report all suspected potential endpoints for adjudication by the CEC.

Events for adjudication should be reported as soon as critical data (as defined in the eCRF page) to the event adjudication is available. A query will be posted for events that require additional supporting documentation from the sites in order to render an adjudicated result and will be followed up by the sponsor. Every effort will be made to provide the CEC with clean eCRF data and required clinical data prior to event adjudication.

9.4.3.2 NYHA class assessment

NYHA class	Symptoms
I	Patients with cardiac disease but without resulting limitation of physical activity. Ordinary physical activity does not cause undue fatigue, palpitation, dyspnea, or anginal pain.
II	Patients with cardiac disease resulting in slight limitation of physical activity. They are comfortable at rest. Ordinary physical activity results in fatigue, palpitation, dyspnea, or anginal pain.
III	Patients with cardiac disease resulting in marked limitation of physical activity. They are comfortable at rest. Less than ordinary activity causes fatigue, palpitation, dyspnea, or anginal pain.
IV	Patients with cardiac disease resulting in inability to carry on any physical activity without discomfort. Symptoms of heart failure or the anginal syndrome may be present even at rest. If any physical activity is undertaken, discomfort is increased.

Source: (45)

9.4.4 Patient-reported outcomes

At study visits where the questionnaire is required (see [Table 9–1](#)), patients should complete it before any other study procedures or assessments.

At collection, the questionnaire will be reviewed for completeness, and the patient will be encouraged to answer any blank data fields. Subsequently, a member of the investigator's team will enter the responses into the eCRF. Details about scoring and calculating algorithms will be provided in the SAP.

[figure not shown]
9.4.4.1 KCCQ

The **KCCQ** is the leading health-related quality-of-life measure for patients with CHF. It was developed in the late 1990s to early 2000s by [name] at the Mid-America Heart Institute, Kansas City, MO, USA. It is a 23-item questionnaire that independently measures the impact of patients' HF, or its treatment, on 7 distinct domains:

- 1) Symptom Frequency – the KCCQ Symptom scale quantifies the frequency of clinical symptoms in HF, including fatigue, shortness of breath, paroxysmal nocturnal dyspnea, and edema / swelling.
- 2) Symptom Burden – the KCCQ Symptom burden scale quantifies the severity of clinical symptoms in HF, including fatigue, shortness of breath and edema / swelling.
- 3) Physical Limitation – the KCCQ Physical limitation scale measures the limitations patients experience, due to their HF, in performing routine activities.
- 4) Quality of Life – the KCCQ Quality of life scale is designed to reflect patients' assessment of their quality of life, given the current status of their HF.
- 5) Social Limitations – the KCCQ Social limitation scale quantifies the extent to which HF symptoms impair patients' abilities to interact in social roles.
- 6) Self-efficacy – numerous studies have underscored the importance of patients being engaged in the management of their disease. The KCCQ Self-efficacy scale quantifies patients' perception of how to prevent HF exacerbations and manage complications when they arise.
- 7) Symptoms Stability– unlike the other 5 domains that provide cross-sectional quantification of patients' current status, the KCCQ Symptom stability domain measures recent changes in patients' symptoms. As a measure of change, it is most interpretable as a baseline assessment of the stability of patients' symptoms at the start of the study and thereafter.

In addition, there are 3 summary scores, a Total Symptom Score that combines the Symptom Frequency and the Symptom Burden scores, a Clinical Summary Score that combines the Total Symptom and Physical Limitation scores to replicate the NYHA classification; and an Overall Summary Score that includes the Total Symptom, Physical Limitation, Social Limitations, and Quality of Life scores ([Figure 9–1](#)).

Figure 9–1: KCCQ Scores

9.4.4.2 EQ-5D-5L

The EQ-5D-5L consists of 2 pages: the EQ-5D-5L descriptive system and the EQ visual analogue scale (EQ VAS). The EQ-5D-5L descriptive system comprises 5 dimensions: mobility, self-care, usual activities, pain / discomfort, and anxiety / depression. Each dimension has 5 levels: no problems, slight problems, moderate problems, severe problems and extreme problems. The respondent is asked to indicate his / her health state by ticking (or placing a cross) in the box against the most appropriate statement in each of the 5 dimensions.

The EQ VAS records the respondent’s self-rated health on a vertical, visual analogue scale where the endpoints are labeled ‘the best health you can imagine’ and ‘the worst health you can imagine’. This information can be used as a quantitative measure of health outcome as judged by the individual respondents.

9.5 Pharmacokinetics / pharmacodynamics

It is planned to collect PK samples from all patients randomized. The data collected are intended to be used for PK analysis of the study population as a whole and should also give information about individual exposure to BAY 84-3174. Only the active metabolite BAY 84-3174 will be measured from the plasma samples collected (see Section 7.2 for details regarding different BAY numbers).

A sparse sampling schema has been developed, which will allow for a limited number of PK samples to be obtained from each patient. The sampling time points have been included in the flow chart (see Table 9–1). The PK sampling schedule is detailed in the visit description (Section 9.2). It is important to exactly record in the patient’s file the time point when the PK sample is taken, as well as the times of the most recent medication intake prior to the blood sampling. The sampling variability will be used for modelling the PK and PD characteristics of the study medication.

Details about the collection, processing, storage and shipment of samples will be provided separately (e.g. sample handling sheets or laboratory manual).

9.6 Safety

9.6.1 Adverse events

9.6.1.1 Definitions

Definition of adverse event (AE)

In a clinical study, an AE is any untoward medical occurrence (i.e. any unfavorable and unintended sign [including abnormal laboratory findings], symptom or disease) in a patient or clinical investigation subject after providing written informed consent for participation in the study. Therefore, an AE may or may not be temporally or causally associated with the use of a medicinal (investigational) product.

A surgical procedure that was planned prior to the start of the study by any physician treating the patient should not be recorded as an AE (however, the condition for which the surgery is required may be an AE).

In the following differentiation between medical history and AEs, the term “condition” may include abnormal physical examination findings, symptoms, diseases, laboratory, or ECG findings.

- Conditions that started before signing of informed consent and for which no symptoms or treatment are present until signing of informed consent are recorded as medical history (e.g. seasonal allergy without acute complaints).
- Conditions that started before signing of informed consent and for which symptoms or treatment are present after signing of informed consent, at unchanged intensity, are recorded as medical history (e.g. allergic pollinosis).
- Conditions that started or deteriorated after signing of informed consent will be documented as adverse events.

Definition of serious adverse event (SAE)

An SAE is classified as any untoward medical occurrence that, at any dose, meets any of the following criteria (a – f):

- a. Results in death
- b. Is life-threatening

The term ‘life-threatening’ in the definition refers to an event in which the patient was at risk of death at the time of the event, it does not refer to an event which hypothetically might have caused death if it were more severe.

- c. Requires inpatient hospitalization or prolongation of existing hospitalization

A hospitalization or prolongation of hospitalization will not be regarded as an SAE if at least one of the following exceptions is met:

- The admission results in a hospital stay of less than 12 hours
- The admission is pre-planned

- (e.g. elective or scheduled surgery arranged prior to the start of the study; admission is part of the study procedures as described in Section 9.2)
- The admission is not associated with an AE (e.g. social hospitalization for purposes of respite care).

However, it should be noted that invasive treatment during any hospitalization may fulfill the criterion of ‘medically important’ and as such may be reportable as an SAE dependent on clinical judgment. In addition, where local regulatory authorities specifically require a more stringent definition, the local regulation takes precedence.

d. Results in persistent or significant disability / incapacity

Disability means a substantial disruption of a person’s ability to conduct normal life’s functions.

e. Is a congenital anomaly / birth defect

f. Is another serious or important medical event as judged by the investigator

Definition of treatment-emergent adverse event

An AE is classified as treatment-emergent if it occurs or worsens after the first dose of study drug up to 6 weeks after the last dose of study drug.

9.6.1.2 Classifications for adverse event assessment

All AEs will be assessed and documented by the investigator according to the categories detailed below.

9.6.1.2.1 Seriousness

For each AE, the seriousness must be determined according to the criteria given in Section 9.6.1.1.

9.6.1.2.2 Intensity

The intensity of an AE is classified according to the following categories:

- Mild - usually transient in nature and generally not interfering with normal activities
- Moderate - sufficiently discomforting to interfere with normal activities
- Severe - prevents normal activities

9.6.1.2.3 Causal relationship

The assessment of the causal relationship between an AE and the administration of treatment is a decision to be made by the investigator, who is a qualified physician, based on all information available at the time of the completion of the CRF.

The assessment is based on the question whether there was a “reasonable causal relationship” to the study treatment in question.

Possible answers are “yes” or “no”.

An assessment of “no” would include:

1. The existence of a highly likely alternative explanation, e.g. mechanical bleeding at surgical site.

or

2. Non-plausibility, e.g. the patient is struck by an automobile when there is no indication that the drug caused disorientation that may have caused the event; cancer developing a few days after the first drug administration.

An assessment of “yes” indicates that the AE is reasonably associated with the use of the study treatment.

Factors to be considered in assessing the relationship of the AE to study treatment include:

- The temporal sequence from drug administration: The event should occur after the drug is given. The length of time from drug exposure to event should be evaluated in the clinical context of the event.
- Recovery on drug discontinuation (de-challenge), recurrence on drug re-introduction (re-challenge): Patient’s response after de-challenge or re-challenge should be considered in view of the usual clinical course of the event in question.
- Underlying, concomitant, intercurrent diseases:
Each event should be evaluated in the context of the natural history and course of the disease being treated and any other disease the patient may have.
- Concomitant medication or treatment:
The other drugs the patient is taking or the treatment the patient receives should be examined to determine whether any of them might have caused the event in question.
- Known response pattern for this class of drug.
- Exposure to physical and / or mental stresses: The exposure to stress might induce adverse changes in the recipient and provide a logical and better explanation for the event
- The pharmacology and pharmacokinetics of the study treatment:
The pharmacokinetic properties (absorption, distribution, metabolism and excretion) of the study treatment, coupled with the individual patient’s pharmacodynamics should be considered.
- The assessment is not possible.

Causal relationship to protocol-required procedure(s)

The assessment of a possible causal relationship between the AE and protocol-required procedure(s) is based on the question whether there was a “reasonable causal relationship” to protocol-required procedure(s).

Possible answers are “yes” or “no”.

9.6.1.2.4 Action taken with study treatment

Any action on study treatment to resolve the AE is to be documented using the categories listed below.

- Drug withdrawn
- Drug interrupted
- Dose not changed
- Not applicable
- Unknown

9.6.1.2.5 Other specific treatment(s) of adverse events

- None
- Remedial drug therapy
- Other

9.6.1.2.6 Outcome

The outcome of the AE is to be documented as follows:

- Recovered / resolved
- Recovering / resolving
- Recovered / resolved with sequelae
- Not recovered / not resolved
- Fatal
- Unknown

9.6.1.3 Assessments and documentation of adverse events

The investigator has to record on the respective CRF pages all adverse events occurring in the period between the signing of the informed consent and the end of the follow-up phase; after the end of the follow-up phase there is no requirement to actively collect AEs including deaths. The type of information that should be assessed and recorded by the investigator for each AE is listed in Section [9.6.1.2](#).

“Death” should not be recorded as an AE on the AE page. Instead, “death” is the outcome of an underlying AE(s).

For all serious adverse events (SAEs) the sponsor has to carry out a separate assessment for expectedness, seriousness and causal relationship to study drug.

9.6.1.4 Reporting of serious adverse events

The definition of serious adverse events (SAEs) is given in Section [9.6.1.1](#). Each SAE must be followed up until resolution or stabilization by submission of updated reports to the designated recipient.

If an SAE is unexpected, i.e. the event is not previously documented in the investigator's brochure (IB) (new occurrence) and is suspected to be related to the study drug, this event is considered a Suspected Unexpected Serious Adverse Reaction (SUSAR). In general, SUSARs will be unblinded by the sponsor for regulatory reporting (see below for exceptions).

Investigator's notification of the sponsor

All investigators will be thoroughly instructed and trained on all relevant aspects of the investigator's reporting obligations for SAEs. This information, including all relevant contact details, is summarized in the investigator site file. This information will be updated as needed.

The investigator must report immediately (within 24 hours of the investigator's awareness) all SAEs occurring during the observation period defined in Section 9.6.1.3 to the recipient detailed in the instructions for SAE reporting included in the Investigator File. For this, an AE page and the complementary SAE pages in the CRF must be completed for each SAE.

SAEs occurring after the protocol-defined observation period will be processed by the sponsor according to all applicable regulations.

Notification of the IECs / IRBs

Notification of the IECs / IRBs about all relevant events (e.g. SAEs, SUSARs) will be performed by the sponsor and / or by the investigator according to all applicable regulations.

Notification of the authorities

The processing and reporting of all relevant events (e.g. SAEs, SUSARs) to the authorities will be done by the sponsor according to all applicable regulations.

Sponsor's notification of the investigational site

The sponsor will inform all investigational sites about reported relevant events (e.g. SUSARs) according to all applicable regulations.

Protocol-specific exceptions to SAE unblinding / reporting

If reported as SUSARs, the following clinical events will be exempted from unblinding and expedited reporting by the sponsor to investigators, IECs / IRBs, and regulatory agencies, since they are considered, consistent with the underlying condition, as disease related in the defined study population:

- CV death
- Worsening of heart failure
- Non-fatal myocardial infarction
- Non-fatal stroke
- Transient ischemic attack
- Cardiac arrhythmias
- Coronary revascularization procedures.

Note that all of these events will be reviewed and monitored by an external DMC unblinded to treatment as part of the overall assessment of safety and efficacy for neladenoson bialanate. Based upon their regular review of unblinded safety results, the DMC is empowered to make recommendations with regard to trial conduct to assure the continuing appropriate safety of the subjects participating in the study.

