Heart failure is often associated with comorbidities like CKD and diabetes in HFrEF and HFpEF patients (30). Renal effects of adenosine A1R activation lead to vasoconstriction of the afferent arterioles in the kidneys (31) and thereby sodium retention and anti-diuretic effects. The effects were regarded as potential for renal benefit with adenosine antagonism in HF and led to large scale drug development programs with adenosine A1R antagonists, such

as rolofylline in patients with acute decompensated heart failure (ADHF). But the Phase III trial failed to show any renal protection. Instead, higher rates of persistent renal impairment, seizure and stroke were noted in the rolofylline group (32, 33). In contrast, an A1R agonist shows reno-protective effects in preclinical models of ischemia-induced renal injury (34). Increased plasma levels of free fatty acids (FFAs) are often found in patients with HF (35, 36) and result in an increase of insulin resistance and might be involved in the deterioration of heart function. A1R agonists can reduce plasma levels of FFAs in humans as shown in clinical trials (37). Furthermore, FFAs act as substrate for the energetic metabolism in the heart. HF is characterized by an added reliance on fatty acid oxidation, with downregulation of myocardial glucose transporters (38, 39). These changes characterize the transition of the failing heart to a fetal metabolic phenotype and gene profile, an adaptation that can further promote HF progression (38-40). Animal studies suggest that partial A1R agonist capadenoson can augment expression of the GLUT-1 and GLUT-4 glucose transporters to near normal levels (15). Moreover, therapy with capadenoson has also been associated with normalization of protein levels that mediate fatty acid oxidation (15). Thus, A1R agonism appears capable of partially correcting derangements in cardiac substrate utilization and restoring a physiologic metabolic profile in HF.

Previous attempts to address the A1 receptor, while offering potential therapeutic benefits, were limited by undesirable side effects that include bradycardia, atrioventricular blocks, sedation and antidiuretic effects. Furthermore, adenosine-like A1R agonists often have the drawback of a short half-life and low bioavailability making them not suitable for chronic oral therapy.

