3.4 Rationale of the study

The main limitations of using full A1R agonists in cardiovascular indications such as HF are undesired cardiac effects, such as bradycardia and higher degree AV block as well as negative cardiac inotropy and dromotropy. In contrast, preclinical data show that the partial adenosine A1R agonist neladenoson bialanate can be used to modulate and trigger primarily favorable pharmacological responses for HF therapy and avoid undesired effects such as AV conduction abnormalities and higher degree AV Block. Nevertheless, based on the mode of action, there are theoretical concerns particularly with regard to undesired effects, such as bradycardia and higher degree AV block for an A1R agonist, which might be aggravated by concomitant use of standard heart failure therapy.

The purpose of this clinical trial is to assess the safety, tolerability and the pharmacokinetic and pharmacodynamic response of 20 weeks' treatment with neladenoson bialanate compared to placebo in patients with chronic HFrEF on standard therapy for HF and to find the optimal dose for a further Phase III trial.

4. Study objectives

The objective of the study is to find the optimal dose of neladenoson bialanate for the Phase III trial by detecting and characterizing a significant dose-response relationship in the two primary efficacy endpoints, absolute change from baseline in LVEF and log-transformed NT-proBNP at 20 weeks, in patients with chronic heart failure with reduced ejection fraction (HFrEF), and by characterizing the safety, tolerability and pharmacodynamic effects of the compound when given in addition to standard therapy for HFrEF.

An exploratory objective is to further assess pharmacokinetic parameters and blood and urine biomarkers.

[figure not shown]
For variables please see Section [10.3.1](#).

5. Study design

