9.6.1.6 Adverse events of special interest

Adverse events of special interest have to be reported to the sponsor along the timelines set for serious adverse events (even though they may not be classified as serious), i.e. within 24 hours of the investigator's awareness, as described in Section 9.6.1.4.

Adverse events of special interest are:

- Symptomatic bradycardia (HR < 50 bpm)
- Findings in ECG and / or AVIVO device as follows:
 - Mobitz type I AV-block leading to withdrawal or interruption of study drug
 - Mobitz type II AV block leading to withdrawal or interruption of study drug or leading to any change in therapy
 - Third degree AV blocks

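### The SUSAR exemption for cardiac arrhythmias is undefined and makes no exception for bradycardia and AV block, the rhythm events the protocol itself links to the drug's mode of action

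*Protocol*

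**What the plan says.** Protocol 9.6.1.4 sets the general rule that SUSARs are unblinded by the sponsor for regulatory reporting, and then makes protocol-specific exceptions. Seven event types, if reported as SUSARs, "will be exempted from unblinding and expedited reporting by the sponsor to investigators, IECs / IRBs, and regulatory agencies". They are exempt because they are regarded "as disease related in the defined study population". The sixth entry reads, in full, "Cardiac arrhythmias". Section 7.5 (Blinding) refers to 9.6.1.4 for exceptions to SUSAR unblinding.

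Other sections treat some rhythm events as a drug question:

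- Section 3.2 says earlier attempts to address the A1 receptor were "limited by undesirable side effects that include bradycardia, atrioventricular blocks, sedation and antidiuretic effects".
- Section 3.4 raises, because of how the drug acts, "theoretical concerns particularly with regard to undesired effects, such as bradycardia and higher degree AV block for an A1R agonist", and says that standard heart failure therapy might aggravate them.
- Section 9.6.1.6 lists symptomatic bradycardia (heart rate below 50 bpm), Mobitz I and II blocks with stated consequences, and "Third degree AV blocks" without condition. All are reportable to the sponsor within 24 hours even when not serious.
- Section 10.3.1.4 singles out AV blocks among the safety variables, and SAP 6.3.3 repeats the special-interest list.

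Section 9.6.1.4 adds that an external, unblinded DMC reviews all exempt events and may make recommendations on trial conduct.

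**The concern.** An exemption of this kind rests on the premise that the event is background in the population, so a single case says little about the drug. For bradycardia and AV block, the protocol's own rationale gives a reason to doubt that premise. Section 9.6.1.4 nevertheless exempts arrhythmias as a class, without a definition and without mentioning the events of special interest.

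What is at stake is prompt, case-level knowledge. Suppose an investigator reports a serious bradycardia suspected to be drug related, and the sponsor judges it unexpected. The other sites, the ethics committees and the regulators would not receive it as an expedited report. Their patients are on the same drug with the background therapy that the protocol says might aggravate the effect.

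**Working it through.** No calculation applies: the point depends on no rate, error level or sample size, and the documents state no figure on it. The check is a comparison of sections.

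1. **Which events are exempt.** Section 9.6.1.4 gives only the class name. Bradycardia plainly falls within it. AV block falls within it on the ordinary broad reading, but is not named. Section 9.6.3.5 lists bradyarrhythmias and conduction disorders as separate items among what the AVIVO system detects, so the protocol does not settle whether a conduction block counts as an arrhythmia.

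2. **Whether the disease-related reason fits.** Exclusion criterion 9 (section 6.2) bars patients with sustained heart rate below 50 bpm, the same threshold as the bradycardia event of special interest. Criterion 11 bars clinically relevant AV block of grade II or higher unless a pacemaker or ICD/CRTD is in place. These criteria do not make new bradycardia or block on treatment drug related. They do make it harder to attribute to what patients brought into the trial, so the stated reason is weakest for these events.

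3. **How a case travels.** Take a serious, drug-suspected symptomatic bradycardia:
   - Investigator to sponsor: within 24 hours, as a serious event and as an event of special interest (9.6.1.4, 9.6.1.6).
   - Sponsor: its own assessment of expectedness, seriousness and causality (9.6.1.3).
   - If the brochure lists the event: it is not a SUSAR, and the exemption has no bearing.
   - If the brochure does not list it: it is a SUSAR, and the exemption stops both unblinding and expedited onward reporting.
   - DMC: unblinded review, at intervals left to a charter (13.1).

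   The gap is therefore confined to the sponsor's onward reporting, and to events not listed in the brochure.

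4. **Whether the efficacy objective needs the exemption for these events.** Arrhythmias are not among the clinical outcome events collected in section 9.4.3.1 (deaths, HF hospitalizations and urgent HF visits, myocardial infarction, stroke). LVEF is read centrally (9.4.1), and the NT-proBNP samples go to the central laboratory (Table 9–1). The primary endpoints therefore do not depend on keeping the code closed for these cases.

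**The case against.** The strongest reply is that the two rules do not collide. Section 9.6.1.6 governs investigator-to-sponsor reporting, and the exemption governs the sponsor's onward reporting, so both can be followed at once. An event can also be common in a disease and still deserve special interest. This stands: there is no strict contradiction between 9.6.1.4 and 9.6.1.6. What remains is that the reason given for the exemption sits badly with sections 3.2 and 3.4.

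The safeguards are also real. The DMC is external, unblinded and reviews all exempt events. Relevant new safety information goes into a brochure update sent to all sites (9.6.1.5). AVIVO tracings are read around the clock during wear periods, and investigators may unblind in an emergency (7.5). A reader might infer that these events go unmonitored, and the documents do not support that. None of these routes, however, is stated to notify investigators, ethics committees or regulators of individual cases. Section 9.6.1.4 also says that reporting follows applicable regulations, but the protocol-specific exception is the more specific text.

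Three stronger readings should be set aside:

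- A reader might infer that the protocol expects AV block and bradycardia from this drug. Section 3.4 calls the concerns theoretical and says preclinical data indicate that a partial agonist can avoid AV conduction abnormalities and higher degree AV block. Section 9.6.1.6 does not call its events expected or drug caused.
- A reader might infer that these are the only serious reactions foreseen. Sections 3.2 and 3.4 also mention sedation, antidiuretic effects, and negative inotropy and dromotropy in connection with earlier or full agonists.
- A reader might infer that extra unblinding would be rare and harmless to the analysis. The documents give no event rate. Central reading does not remove every route to bias: per-protocol membership depends on adherence (SAP 5.1), and HF hospitalization or CV death can lead to worst-case imputation (SAP 6.2.1.2), so site decisions after unblinding could matter.

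**Conclusion.** The point holds as a gap in the safety-reporting rules. Followed as written, section 9.6.1.4 stops expedited onward reporting of a serious, unexpected, drug-suspected bradycardia and, on the ordinary reading of an undefined term, of a high-degree AV block. The disease-related reason is least convincing for exactly these events.

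This rests on two assumptions. First, the investigator's brochure does not already list the events; if it does, they are not SUSARs and the exemption changes nothing for them. Second, AV block counts as a cardiac arrhythmia; if the sponsor means otherwise, the protocol should say so.

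The number of affected cases cannot be estimated from the documents. The effect of unblinding such cases on the centrally read primary endpoints should be small, but it is not quantified. Given the DMC and the 24-hour route to the sponsor, this is a change that should be made, not evidence that patients are unprotected.

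**What to change.** Reconcile section 9.6.1.4 with sections 3.4 and 9.6.1.6 by two additions to the exceptions list:

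- Define the term cardiac arrhythmias, saying whether conduction disorders are included.
- State that bradycardia and AV block events of the type listed in 9.6.1.6 are not covered by the exemption. Keep the exemption for other arrhythmias.

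The wording needs care at one boundary. Mobitz I and II blocks are events of special interest only with specified consequences, so a bare cross-reference to 9.6.1.6 would leave a serious Mobitz block without those consequences exempt. The text should say whether that is intended.

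The drafting cost is a line or two in 9.6.1.4; section 7.5 already refers there. The operational cost is that some individual cases are unblinded for regulatory reporting. If the brochure already lists these events, the carve-out costs nothing.
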